6.3 SUBJECT SETS ANALYSED

From CTP Section 7.3:

There will be 4 main patient populations in this trial for analyses: the randomized set (RS), the safety analysis set (SAF), the modified RS (m-RS), and the per-protocol set (PPS).

Randomized Set (RS)

This patient set includes all randomized patients. Treatment assignment will be as randomized. This is the main analysis set for presentation of efficacy on binary endpoints.

Safety Analysis Set (SAF)

This patient set includes all patients who were randomized and received at least one dose of study drug. It will be the main analysis set for presentation of safety. Patients will be analyzed according to the actual treatment.

Modified Randomized Set (m-RS)

This patient set includes all patients in the RS who had a baseline and at least one post-baseline measurement for the endpoint under consideration. Treatment assignment will be as randomized. This is the main analysis set for presentation of efficacy on continuous data, e.g. IBDQ.

Per-Protocol Set (PPS)

This patient set includes all patients in the RS who adhered to the CTP without any iPDs (potentially affecting the study outcome) which lead to exclusion from the PPS. This set will be used for sensitivity analysis on the primary efficacy endpoint.

In addition, the following patient sets will be defined for analysis.

Enrolled set (ES)

This patient set includes all patients who signed informed consent. It will be used for analyses of patient disposition.

For the first interim database snapshot, modified versions of the ES, RS, SAF, and m-RS will be defined: the ES_i, RS_i, the SAF_i, and the m-RS_i. Each of the modified patient sets will include those patients from the original set who completed/discontinued through the week 12 visit on or prior to the cut-off date (see Section 3). Each of these modified patient sets will be handled according to the same procedures used to derive the full patient sets.

For the analyses to be performed at the time of the second interim database snapshot (when all randomized patients have completed/discontinued through week 12), and at the time of the final, updated trial analysis, the ES, RS, SAF, m-RS, and PPS will be used. Corresponding

analyses performed at the time of the first interim database snapshot will use the ESi, RSi, SAFi, and m-RSi.

The discussion of all exceptional cases and problems and the decisions on the allocation of patients to populations will be made at latest at the DBLM. A separate DBLM will be performed prior to each database snapshot of this trial.

Handling of Treatment Misallocations in Analysis Sets

If a subject is randomized but not treated, they will be reported under their randomized treatment group for efficacy analysis according to RS, m-RS, and PPS (per the intent-to-treatment principle). By definition, however, such patients are excluded from the safety analyses as no study medication was taken.

If a subject is treated but not randomized, they will be excluded from both efficacy analysis and safety analysis by definition. However, subjects under such circumstances will be summarized in the final clinical trial report.

If a subject is randomized but took incorrect treatment during the study, then:

- For efficacy analyses according to RS, m-RS, and PPS, they will be reported under their randomized treatment groups. But if the subject has an iPD as defined in [Section 6.2](#), the subject will be excluded from PPS for efficacy analysis.
- For safety analyses using the SAF,
 - if a subject is planned with multiple dose administrations of BI 655130 (randomized to 450mg q4w, 1200mg q4w), they will be reported under their randomized treatment group for safety analysis because the overall safety profile will be driven by the amount of drug received in totality over the entire treatment duration. It is not likely that the safety profile will deviate from the planned treatment regimen if the subject receives only one or two vials of the incorrect medication at only some dosing occasions.
 - if a subject is planned with a single dose administration of BI 655130 (randomized to 300mg SD), they will be reported under BI 655130 300mg SD if the subject receives at least one dose of BI 655130 at any visit. A subject will be assigned to the placebo treatment group only if they don't receive any BI 655130 during the entire treatment period.
 - if a subject is planned with placebo treatment, they will be reported under placebo if no treatment with BI 655130 is received at any visit. If the subject receives $> = 1$ vial ($> = 150$ mg) of BI 655130 during the entire treatment duration, they will be reported as BI 655130 300mg SD treatment group.

[Table 6.3: 1](#) (first interim database snapshot), [Table 6.3: 2](#) (second interim database snapshot), and [Table 6.3: 3](#) (final trial snapshot) illustrates the data sets which are to be used

for each category class of endpoints, and the approaches used with regard to missing data. For explanation of the different methods of handling missing data see [Section 6.6](#).

Table 6.3: 1 Subject sets analysed (first interim database snapshot)

Class of endpoint	Patient set			
	ESi	RSi	SAFi	m-RSi
Disposition	√	√		
Compliance		√		
Exposure			√	
iPDs		n.a.		
Demographic/baseline characteristics		√		
Primary efficacy endpoint (primary analysis only)		√		
Secondary efficacy endpoints (Binary) (primary analysis only)		√		
Secondary efficacy endpoints (Continuous) (primary analysis only)				√
Safety parameters			√	
Use of rescue medication		√		

At the time of the first interim database snapshot, only selected analyses on each efficacy endpoint will be done. All safety displays will be produced.

Table 6.3: 2 Subject sets analysed (second interim database snapshot)

Class of endpoint	Patient set				
	ES	RS	SAF	m-RS	PPS
Disposition	√	√			
Compliance		√			
Exposure			√		
iPDs*		√			
Demographic/baseline characteristics		√			
Primary efficacy endpoint		√			√
Secondary efficacy endpoints (Binary)		√			
Secondary efficacy endpoints (Continuous)				√	
Safety parameters			√		
Use of rescue medication		√			

[figure not shown]
*the patient with iPD of treated but not randomized will only be listed in the footnote of the iPD table.

[figure not shown]
At the time of the second interim database snapshot, all analyses per TSAP are scheduled to be performed.

Table 6.3: 3 Subject sets analysed (final, updated trial snapshot)

Class of endpoint	Patient set			
	ES	RS	SAF	m-RS
Disposition	√	√		
Compliance		n.a.		
Exposure			n.a.	
iPDs		n.a.		
Demographic/baseline characteristics		n.a.		
Primary efficacy endpoint (primary analysis only)		√		
Secondary efficacy endpoints (Binary) (primary analysis only)		√		
Secondary efficacy endpoints (Continuous) (primary analysis only)				√
[REDACTED]				
Safety parameters (selected displays only)			√	
Use of rescue medication		n.a.		

At the time of the final, updated database snapshot, only select analyses of the trial data are to be performed in order to ensure the consistency in key trial conclusions subsequent to the performance of two interim database snapshots.

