3. INTRODUCTION

As per International Conference on Harmonisation (ICH) E9 (1), the purpose of this document is to provide a more technical and detailed elaboration of the principal features of the analysis described in the CTP and its amendments, and to include detailed procedures for executing the statistical analysis of the primary and secondary variables and other data.

This trial statistical analysis plan (TSAP) assumes familiarity with the clinical trial protocol (CTP). In particular, the TSAP is based on the planned analysis specification as written in CTP Section 7 “Statistical Methods and Determination of Sample Size”. Therefore, TSAP readers may consult the CTP for more background information on the study, e.g., on study objectives, study design and population, treatments, definition of measurements and variables, planning of sample size, randomisation.

This trial consists of 2 parts, Part 1 to demonstrate proof of concept of clinical activity as an induction therapy in ulcerative colitis (UC), and Part 2 to confirm the efficacy and safety of BI 655130 as an induction treatment in UC. For the purpose of statistical analysis, both parts will be treated as two independent parts whereby the false positive rate is separately controlled within each part. Only patients randomized into Part 1 will be included in the statistical analyses of Part 1 data. This TSAP contains the analysis specification for the final analysis of Part 1.

For further details on the subjects sets thus defined, refer to [Section 6.3](#). For further details on the data to be included into the week 12 analysis, refer to [Table 6.7: 1](#). A logistics and access plan, which will describe any measures used to protect the blind and integrity of the ongoing trial, will be finalized prior to database snapshot and treatment unblind.

Per CTP, a subsequent interim database snapshot will be done based upon the complete 12-week data using all patients randomized into the trial. At this time, all displays as described in this TSAP will be produced. The results from this analysis will be used for potential authority interactions, if applicable.

[figure not shown]
A final, updated analysis of the trial will be performed once all patients have completed the trial. For more details, please refer to [Section 6.3](#).

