The first interim database snapshot and analysis of Part 1, will be performed based upon those randomized patients in Part 1 who have completed/discontinued through the planned first 12 weeks of trial up to the cut-off date (see [Section 6.3](#)). The following data will be used in this analysis:

- Selected summaries of the 12-Week data will be summarized up to the minimum of the (analysis-specific data cut-off; study day 99), unless otherwise specified.

For the second interim database snapshot (the primary analysis per the CTP), to be performed once all randomized patients have completed/discontinued through the planned first 12 weeks of trial (per CTP specification), the following data will be used:

- All 12-Week data will be summarized up to the minimum of the (analysis-specific data cut-off; study day 99), unless otherwise specified.

The final, updated analysis of the trial, will be performed once all patients have completed the trial. Generally only listings of the trial data are planned to be done, however, updates on the primary and secondary endpoint analysis, as well as select AE displays will be produced in order to confirm the consistency of the results to those results obtained at the previous interim snapshots. Any clinical relevant changes from the previous interim analyses to the final analysis will be addressed in the CTR.

Treatment groups for analysis are listed as follows:

- **"Placebo"**
- **"Speso 300 mg IV SD"**
- **"Speso 450 mg IV q4w"**
- **"Speso 1200 mg IV q4w"**
- **"Speso Total"** (across all BI treatment arms)
- **"Overall Total"**(across treatments), where appropriate.

"Overall Total" is applicable in disposition, demographics and baseline characteristics, compliance summaries and safety tables. "BI Total" should also be presented in safety tables.

More details on the technical implementation of these analyses are provided in the ADS Plan of this TSAP.

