6.6.2 Efficacy endpoints

Based on the different reasons for patients' data missing for different endpoints, various approaches will be used to assess the impact of missing data on the efficacy endpoints of this trial, depending upon the type of the endpoint. Approaches to be applied are described below.

Missing data imputations will be performed using all available on-treatment data observed up to the respective analysis cut-off date.

Binary efficacy endpoints

With regards to the handling of missing data on binary efficacy endpoints, the following table gives an overview of the proposed imputation methods which are described in more detail below.

Table 6.6.2: 1 Missing data approaches for binary efficacy endpoints

	Binary efficacy outcome observed or not	Imputation Approach Subsequent to Event of Type		Missing due to Other reasons - Withdrew consent - Loss of follow up - Data not collected - etc.
		Rescue intake	Death due to any cause	
NRI	Observed	NRI	n.a.	n.a.
	Not observed	NRI	NRI	NRI
MI	Observed	MI	n.a.	n.a.
	Not observed	MI	MI	MI
MI-NRI	Observed	NRI	n.a.	n.a.
	Not observed	NRI	NRI	MI
OC	Observed	no imputation	n.a.	n.a.
	Not observed	no imputation	no imputation	no imputation

Primary Imputation Approach – No Response Imputation [NRI]

1. If a patient takes a rescue medication (as defined in [Section 5.4.5](#)) for the treatment of ulcerative colitis or died due to any cause prior to observing the primary endpoint for this trial, then all data subsequent to the intake of such rescue will be considered to be missing.
2. For endpoints which are measured at multiple visits (thereby excluding the endpoints which are based upon the endoscopic subscore), if there are data at visits both before and after the visit with a missing outcome, then impute as success only if both neighbouring visits also represent a success (independent of whether the preceding and following observations were selected for analysis based on time windows described in [Section 6.7](#)) with no intervening use of rescue medication;

For all patients with a missing visit outcome, impute as a failure to achieve a response.

Other Imputation Approaches

- Observed cases (OC) approach: first, set all data collected after intake of a rescue medication to missing; then include all collected data with no imputation performed on the missing data. The analysis using OC approach is only based on all patients who have non-missing values in the patient set.

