7. PLANNED ANALYSIS

The following analyses are planned at different stages throughout Part 1 of this trial.

Part 1 – First Interim Database Snapshot - Week 12 Analysis

The analysis will be performed using all randomized patients who completed/ discontinued through the week 12 visit on or prior to the cut-off date (see Section 3). A database snapshot will then be done. At this time, an interim analysis of the efficacy and safety data through Week 12 will be performed by the sponsor.

The individual patient cut-off date for inclusion of data into the analysis is the minimum of the analysis-specific data cut-off, or study day 99, as described in [Table 6.7: 1](#).

The analyses as described in Section 6.3 of this TSAP will be performed using the subject sets of ESi, RSi, m-RSi, and SAFi.

Part 1 – Second Interim Database Snapshot - Week 12 Primary Analysis (All Randomized Patients)

The analysis will be performed using all randomized patients who completed/ discontinued through the week 12 visit. A database snapshot will then be done. At this time, the complete, primary analysis of all efficacy, safety, and PK/ADA data will be done through Week 12, and will be performed by the sponsor; biomarker data will be reported, if available.

The individual patient cut-off date for inclusion of data into the analysis is the minimum of the analysis-specific data cut-off, or study day 99, as described in [Table 6.7: 1](#).

The analyses as described in Section 6.3 of this TSAP will be performed using the subject sets of ES, RS, m-RS, SAF, and PPS.

Part 1 – Updated analysis after final DBL

A final database lock will be done when all randomized patients in Part 1 complete the trial. A majority of the trial patients are expected to roll-over into the extension trial at Week 12. The analyses as described in Section 6.3 of this TSAP will be performed, up to week 12, using the subject sets of ES, RS, m-RS, and SAF. Selected safety summaries including all data up to the REP, will also be generated.

General Remarks

The format of the listings and tables will follow the BI guideline "Reporting of clinical trials and project summaries" (001-MCG-159) ([9](#)).

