7.4 PRIMARY ENDPOINT

The Multiple Comparison Procedures and Modeling (MCP-Mod) approach ([10](#), [11](#)) is implemented in two main steps: (1) trial design stage; (2) trial analysis stage. The procedures for the trial design stage, including the selection of candidate models covering a suitable range of dose-response shapes and sample size and power calculations, are provided in the CTP Section 7.3.1 and 7.7. The procedures for the trial analysis stage are specified below.

The primary endpoint of the clinical remission is binary in nature. The estimate of response rate from each dose group is obtained via logistic regression without intercept. In case 0 event is observed in one of the dose groups, a penalized regression based on the Firth's bias reduction method ([21,22](#)) will be used. The subsequent MCP-Mod analysis are based on the response rate on the logit scale.

The doses which are included in Part 1 are placebo, and BI 655130 300 mg SD, 450 mg q4w, and 1200 mg q4w. The primary dose-response analysis of the clinical remission, based on the RS, will use MCP-Mod, and each dose regimen will be described via the appropriate q4w regimen administered over the 12 week treatment period (i.e. 300 mg SD will be approximated by 100 mg q4w; 450 mg q4w and 1200 mg q4w doses will remain unchanged) under the assumption that the cumulative concentrations over time (AUC) and thus the cumulative total dose is the key driver of the efficacy response in the modelling part of MCP-Mod. The response rate for each dose group using NRI as the primary missing data handling approach (see [Section 6.6](#)), as well as the variance-covariance matrix for the primary endpoint are estimated by the data.

The multiple comparison procedure will then be implemented using optimal contrast tests which control the family-wise type I error rate at a one-sided $\alpha = 0.20$. The optimal contrasts corresponding to the candidate models are calculated as in the trial design stage and shown in [Table 7.4: 1](#). In the trial analysis stage, these optimal contrasts will be updated using the expected model means from the candidate set and the estimated variance-covariance matrix from the collected data. The updated contrast coefficients will be described in the final CTR.

Table 7.4: 1 Contrast coefficients

Model	Contrast coefficients for dose			
	Placebo	300 mg BI SD	450 mg BI q4w	1200 mg BI q4w
Linear	-0.395	-0.352	-0.096	0.843
E _{max}	-0.858	0.178	0.325	0.355

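### If the first-snapshot cut-off fell while patients were still within about 12 weeks of randomisation, RSi admits only the discontinuers among them, which lowers the remission rates

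*SAP*

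**What the plan says.** SAP 6.3 defines reduced versions of four sets (ESi, RSi, SAFi, m-RSi) for the first snapshot, limited to patients "who completed/discontinued through the week 12 visit on or prior to the cut-off date". SAP 6.1 puts the same condition as "those randomized patients in Part 1 who have completed/discontinued through the planned first 12 weeks of trial up to the cut-off date", and SAP 7 as "using all randomized patients who completed/ discontinued through the week 12 visit on or prior to the cut-off date". Sections 6.3 and 7 refer to Section 3 for the cut-off. The published Section 3 resumes after a gap with "For further details on the subjects sets thus defined, refer to", so the cut-off, and anything attached to it, cannot be read. That gap comes from publication and is not a fault in the plan.

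Table 6.3: 1 assigns the primary analysis of clinical remission to RSi. SAP 7.4 runs it by MCP-Mod, "using NRI as the primary missing data handling approach". SAP 6.6.2 gives the rule: "For all patients with a missing visit outcome, impute as a failure to achieve a response". The softer option in 6.6.2, which borrows from neighbouring visits, excludes endpoints that use the endoscopic subscore and so does not apply to clinical remission. Table 6.7: 1 plans the Week 12 visit for day 85 and closes its extended window at day 99, or at the cut-off if that is earlier.

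The second snapshot uses all randomised patients, and SAP 6.1 identifies it as the protocol's primary analysis.

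**The concern.** Take two patients randomised six weeks before the cut-off. Neither can have a Week 12 visit. The one who has discontinued satisfies the condition and enters RSi as a failure. The one still on treatment does not satisfy it and is left out. Among recently randomised patients, membership of the set therefore depends on something closely tied to the outcome.

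What is at stake is how the first look reads. Each arm's remission rate would be too low, and the modelled difference from placebo, which SAP 7.4 compares with 0.16, would be off. The proportion of discontinuers shown for RSi would be too high. In m-RSi (IBDQ, analysed by MMRM) these patients are not scored as failures, but the mix of patients is altered in the same way.

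**Working it through.** **Step 1: the plan's own figure.** Protocol Table 7.7.1:1 gives a Part 1 success probability of 0.672 (rates 0.15/0.25/0.30/0.35, 40 per arm, threshold 0.16). A re-simulation gives 0.672. It used the five candidate shapes on the logit scale, a one-sided 0.20 maximum-contrast test, the lowest AIC among significant models, and 8,000 runs. The same simulation does not match the 0.11-threshold row (0.877 against 0.836); that row is not used here.

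**Step 2: inputs.** From protocol 7.7.1: remission 0.35 at the high dose and 0.15 on placebo. Not in the documents, so assumed:
- constant accrual up to the cut-off, C weeks after the first randomisation;
- a proportion d discontinuing before Week 12, evenly over the 12 weeks;
- Week 12 status settled at exactly 12 weeks.

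**Step 3: formula.** In units of the weekly accrual rate, patients with at least 12 weeks since randomisation number C − 12, and all are in RSi. A patient randomised t weeks before the cut-off (t < 12) has discontinued with probability d·t/12. Averaged over the last 12 weeks this is d/2, so 12·d/2 = 6d such patients enter, all as failures. For a true rate p under non-response imputation:

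expected RSi rate = p·k, with k = (C − 12)/(C − 12 + 6d).

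**Step 4: results with equal discontinuation in the two arms.**

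| C (weeks) | d | k | true 0.35 | true 0.15 | difference |
|---|---|---|---|---|---|
| 26 | 5% | 14/14.3 = 0.979 | 0.343 | 0.147 | 0.196 |
| 26 | 10% | 14/14.6 = 0.959 | 0.336 | 0.144 | 0.192 |
| 26 | 20% | 14/15.2 = 0.921 | 0.322 | 0.138 | 0.184 |
| 52 | 5% | 40/40.3 = 0.993 | 0.347 | 0.149 | 0.199 |
| 52 | 10% | 40/40.6 = 0.985 | 0.345 | 0.148 | 0.197 |
| 52 | 20% | 40/41.2 = 0.971 | 0.340 | 0.146 | 0.194 |

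With unequal discontinuation the extremes are at C = 26:
- active 20%, placebo 5%: 0.3224 − 0.1469 = 0.1755, about 0.176;
- active 5%, placebo 20%: 0.3427 − 0.1382 = 0.2045, about 0.205.

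Outside this range the effect can be larger. At C = 18 and d = 30%, k = 6/7.8 = 0.769, which gives 0.269 against 0.115, a difference of 0.154.

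**Step 5: share of discontinuers in RSi.** This is (d(C − 12) + 6d)/(C − 12 + 6d). At C = 26, a true 10% appears as 2.0/14.6 = 13.7%, and a true 20% as 4.0/15.2 = 26.3%.

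**Step 6: effect on the 0.16 criterion (illustration).** With 30 mature patients per arm the simulated success probability is 0.673. Adding 1, 2 or 3 early discontinuers per arm gives 0.662, 0.643 and 0.605. This was approximated by 30 + x patients at rates multiplied by 30/(30 + x). Simulation error is about 0.006 per figure (6,000 runs), so the first step is not distinguishable from noise. The third corresponds to a share of 3/33 = 9.1%, slightly above the largest share in the table (1.2/15.2 = 7.9%).

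**Step 7: selection by date.** If entry depends only on the randomisation date, no immature patients are admitted, k = 1 and the difference stays at 0.20. This holds for any limit at or beyond 12 weeks, including day 99.

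**The case against.** The strongest reply is that the deciding text may be hidden. Sections 6.3 and 7 refer to Section 3, where the paragraph that introduced these sets is missing. A randomisation-date condition there would remove the problem. The phrase can also be read as having reached the 12-week point, whether as a completer or a discontinuer; it is used that way for the second snapshot. SAP 6.3 adds that exceptional cases are settled at a database lock meeting before each snapshot. All this makes the point conditional. It does not displace the plain wording, which appears three times without a minimum time since randomisation.

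The second reply is that the effect is small. With 40 per arm the standard error of the difference is √(0.35·0.65/40 + 0.15·0.85/40) = 0.094. The largest shift in the range above is 0.200 − 0.1755 = 0.0245, about a quarter of that, and with fewer patients at a first look the standard error is larger. This stands, and it limits the importance of the point.

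A reader might infer more: that the rates at this snapshot are certainly too low in every arm, or that the trial's efficacy conclusion is compromised. The documents support neither. They show no accrual pattern, cut-off or discontinuation rate, and the bias is zero if randomisation ended about 12 weeks before the cut-off or if no recently randomised patient had discontinued. The primary analysis uses all randomised patients, and the final update repeats it. No visible decision rests on RSi, since SAP Section 3 states that moving seamlessly into Part 2 is no longer viable.

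**Conclusion.** The point holds in conditional form and is minor. On the visible wording, any patient in RSi who was randomised less than about 12 weeks before the cut-off is there because of discontinuation and counts as a non-remitter. The direction for each arm's rate is then known: downward. The contrast shrinks by the same factor when discontinuation is equal across arms and can move either way when it is not.

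The size rests wholly on the accrual and discontinuation assumptions in Step 2. Within them the proportional loss in a rate is about 1% to 8% (k from 0.993 to 0.921). It would be larger if *discontinued* means stopping study drug. Protocol 3.3.4.1 encourages such patients to continue assessments to Week 12, so some could be scored as failures before their Week 12 result was due. Only the first snapshot is touched.

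**What to change.** In SAP 6.3, with matching wording in 6.1 and 7, define RSi and m-RSi by time and not by status. Include every patient of the parent set whose study day 99 (the close of the Week 12 window in Table 6.7: 1) falls on or before the cut-off, whether the patient completed or discontinued. Count from randomisation for anyone never treated. State whether *discontinued* means study drug or trial. If the unreadable part of Section 3 already sets such a date, a cross-reference is enough.

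Leave ESi and SAFi as they are. ESi includes people who were never randomised and have no randomisation date. For safety displays, keeping recent discontinuers is defensible.

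The cost is a few lines of text. Recent discontinuers, and a few Week 12 completers randomised shortly before the limit, wait until the second snapshot, so the first loses a little precision. No data are lost to the primary analysis.
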